8.3. Sample Size Determination

The study will enroll approximately 390 subjects. In two Phase 3 clinical trials with adalimumab (PIONEER I and II; [Kimball et al, 2016a](#)), the proportions of subjects in the placebo control group achieving a HiSCR at Week 12 were 26.0% and 27.6%, respectively. Hence, if the control group only receives placebo, one may assume a HiSCR at Week 12 of approximately 30%. The average HiSCR at Week 12 in the adalimumab groups in PIONEER I and II were 41.8% and 58.9%, respectively with an average of approximately 50% ([Kimball et al, 2016a](#)). The attrition rate throughout the trial is estimated to be approximately 7%. A sample size of approximately 130 subjects per treatment group (390 in total) at a Type I error rate of $\alpha = 0.05$ (two-sided) provides approximately 90% power to detect a 20% superiority of avacopan compared to the placebo control group in HiSCR at Week 12, assuming an HiSCR at Week 12 of 50% in the avacopan group.

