- If both day and month of the start date are missing, the day and month will be imputed with the day and month of the first study dose date if the year is equal to the year of first dose. Otherwise, the month and day is imputed as the first day of the year (01 Jan).

¹⁼For selected endpoints

 If only day is missing, and if the year and month are equal to the first dose date, the day will be imputed as day of the first dose date. Otherwise, the day will be imputed as "01".

D. Multiple Study Centers

No adjustment for stratification by the study centers is planned. However, centers will be grouped by geographic region and a subgroup analysis will be conducted to determine if region impacts the primary endpoint.

E. Covariate Adjustment in Primary Analysis

Continuous variables of the secondary/other efficacy endpoints, change from Baseline to Week 12 in the Sartorius score, modified Sartorius score, IHS4 score, HS-PGA, inflammatory and non-inflammatory nodule count, abscess count, draining, non-draining and total fistula count, total AN count, SF-36 v2 (domains and component scores) and EQ-5D-5L (visual analogue scale and index), HiSQOL, DLQI, and WPAI:SHP will be analyzed using a mixed effects model for repeated measures. This model will include treatment group, visit, treatment-by-visit interaction, and randomization strata (Hurley Stage II or Hurley Stage III, anti-TNF drug use or anti-TNF drug naive) as factors, and corresponding baseline as covariate.

Change from Baseline to Week 12 in WPAI:SHP will be analyzed using an ANCOVA model which includes treatment group, randomization strata (Hurley Stage II or Hurley Stage III, anti-TNF drug use or anti-TNF drug naive) as factors, and corresponding baseline as covariate.

F. Sample Size Reassessment

No sample size reassessment is planned.

G. Interim Analyses or Timing of Analyses

No interim analyses planned.

H. Test Sizes

All confidence intervals will be two-sided with 95% coverage.

I. Multiple Comparisons/Multiplicity

For the primary efficacy endpoint testing, the avacopan 30 mg vs. placebo in HiSCR (H_{11}) and the avacopan 10 mg vs. placebo in HiSCR (H_{12}), a hierarchical procedure will be used to control the overall α at 0.05 level.

That is if H_{11} is rejected at a 2-sided alpha level of 0.05, then the H_{12} will be tested at 2-sided alpha level of 0.05.

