Summary tables for the combined periods using the All Avacopan Treated Population will be presented by the following treatment group:

- Placebo to Avacopan 10 mg
- Placebo to Avacopan 30 mg
- Avacopan 10 mg
- Avacopan 30 mg
- Avacopan Total (i.e., Placebo to Avacopan 10 mg + Placebo to Avacopan 30 mg + Avacopan 10 mg + Avacopan 30 mg)

Continuous data will be summarized with the number of non-missing values, mean, standard deviation, minimum, median, and maximum. Categorical data will be summarized with the number of non-missing values and the numbers of values equal to each of the possible values. Percentages of subjects with each of the possible values will be calculated from the number of subjects in the relevant cohort of the corresponding analysis population, unless stated otherwise. Some continuous variables may also be grouped into categorical levels and evaluated in frequency tables. For efficacy endpoints, such as change and percent change from baseline, if the data is not normal distributed, the logarithmic transformation of the data will be performed prior to analysis, and geometric mean will be presented.

All statistical analyses will be performed using SAS® software, Version 9.3, or higher.

VII. Subject Accountability

A. Subject Disposition

The number of subjects who were screened, who screen failed (by reason), who were randomized, who completed Week 12, Week 36, and Week 44 of the study, respectively, and who withdrew early from the study, along with the reasons for withdrawal, will be presented by treatment group and period. A separate table for analysis populations will also be provided by treatment group.

Patient disposition data will be provided in a listing. A separate listing describing each subject's inclusion or exclusion status for each of the analysis sets will also be provided.

B. Protocol Deviations

Protocol deviations will be captured by the site and reviewed by medical monitor during the study. Classification between CSR reportable and non-CSR reportable protocol deviations will be decided by the study team prior to database lock. All protocol deviations will be listed and summarized by type, treatment group and period.

A listing of protocol deviations will be included.

C. Subject Characteristics

Demographic and Baseline Characteristics

Demographic and baseline information will be summarized for the ITT1 by treatment group:

- Age
- Sex (Male, Female)

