For the analysis of time to loss of response (LOR), the treatment difference between the avacopan 30 mg vs. placebo to avacopan 30 mg, avacopan 10 mg vs. placebo to avacopan 10 mg, avacopan 30 mg group vs. avacopan 10 mg group, and placebo to avacopan 30 mg vs. placebo to avacopan 10 mg will be analyzed using the stratified log-rank test with the baseline Hurley Stage (Stage II vs. III), concomitant antibiotic therapy with allowed antibiotics (Yes vs. No), and anti-TNF drug use (Treatment naïve vs. Previous treatment) as the stratification variables. Subjects without LOR or lost follow-up will be censored at the date of the last assessment of number of HS lesions. Kaplan-Meier curves will be provided by treatment group.

IX. Safety Analyses

Safety analyses will be performed in the Safety Analysis Set using the actual treatment group.

A. Adverse Events

All subjects will be assessed regularly for potential occurrence of adverse events (AEs) throughout the study until the subject is off study. The Medical Dictionary for Regulatory Activities (MedDRA; Version 21.1) will be used to code all adverse events to a System Organ Class (SOC) and Preferred Term (PT).

A treatment-emergent AE (TEAE) in Period 1 is defined as any AE that occurs after the first dose of study treatment in Period 1 and before the date of first dose of study treatment in Period 2.

A treatment-emergent AE (TEAE) in Period 2 is defined as any AE that occurs after the first dose of study treatment in Period 2.

A treatment-emergent AE (TEAE) for all avacopan, is defined as any AE that occurs after the first dose of avacopan treatment in study.

The incidence of TEAEs will be summarized and tabulated by treatment group and period.

The severity of each AE will be assessed as mild, moderate, severe, lifethreatening, fatal, or death. Several occurrences of the same AE in one subject will be counted once and the one with maximum severity will be counted.

The relationship of each AE to the blind study medication will be classified as probably not related or possibly related. Several occurrences of the same AE in one subject will be counted once and the one with the maximum relationship to blind study medication will be counted. If an AE is missing the relationship to blind study medication, the event will be assumed to be probably related for analysis and summarization.

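### The combined-period All Avacopan adverse event tables compare and pool crude percentages over unequal time since first avacopan dose

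*SAP*

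**What the plan says.** **The combined table.** SAP VI.L (Data Display Characteristics) says: "Summary tables for the combined periods using the All Avacopan Treated Population will be presented by the following treatment group". Five columns follow: placebo to 10 mg, placebo to 30 mg, 10 mg, 30 mg, and Avacopan Total, which pools the other four. SAP VI.J defines the population, under its Safety Population heading, as everyone with at least one avacopan dose in either period.

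**The event window.** SAP IX.A defines a treatment-emergent event for all avacopan as "any AE that occurs after the first dose of avacopan treatment in study". No end date is given.

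**The statistic.** SAP IX.A plans the number and percentage of subjects with at least one event. SAP VI.L takes percentages over the number of subjects. Neither document plans person-time rates, a common window from first dose, or time to first adverse event. SAP VII.C summarises exposure for Period 1 and Period 2 separately, so no planned exposure summary matches the combined table.

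**The schedule.** Under Protocol 3.2 and SAP IV.A, subjects first assigned to avacopan take it for 36 weeks. Placebo subjects who complete Period 1 are re-randomised and take it for the 24 weeks of Period 2. All are then followed for 8 weeks off drug.

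**The by-period tables.** SAP IX.A also states: "The incidence of TEAEs will be summarized and tabulated by treatment group and period".

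SAP VI.L does not say that the combined tables hold adverse events. I infer it because the population is a safety population and a separate all-avacopan event definition has no other evident use.

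**The concern.** A percentage of subjects with at least one event grows with the time over which events are counted. Here two columns count over 32 planned weeks and two over 44, side by side and under one total. A reader comparing a continuing column with its switched counterpart at the same dose would see a difference that may reflect calendar time as much as drug effect. Avacopan Total mixes the two windows and estimates the risk at neither.

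What is at stake is the cumulative safety description for the secondary objective of safety from Day 1 to Week 44 (Protocol 2.2, item 4). The relative distortion is largest for uncommon events arising at a steady rate. Some of the events of special interest in Protocol 7.2.3.3 could behave that way.

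**Working it through.** **1. The plan's own figure.** The documents give no adverse event rate for hidradenitis suppurativa and no person-time figure. The one reproducible design figure is the power statement in Protocol 8.3, "provides approximately 90% power to detect a 20% superiority of avacopan": HiSCR 30% against 50%, 130 per group, two-sided alpha 0.05.

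z = [0.20 × √130 − 1.96 × √(2 × 0.40 × 0.60)] / √(0.30 × 0.70 + 0.50 × 0.50) = (2.280 − 1.358) / 0.678 = 1.36, so power is 91.3%. With 121 per group (130 less 7%) it is 89.3%. The figure reproduces and has no bearing on this point.

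**2. Planned windows from first avacopan dose.**

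| Groups | On drug | Plus follow-up | Observed |
|---|---|---|---|
| Placebo to 10 mg, placebo to 30 mg | 24 weeks | 8 | 32 weeks |
| 10 mg, 30 mg | 12 + 24 = 36 weeks | 8 | 44 weeks |

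Because the event window has no end date, the relevant ratio is 44/32 = 1.375 rather than 36/24 = 1.5.

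**3. Same constant hazard in every group.** The incidences are my assumption. With p the incidence at 32 weeks, h = −ln(1 − p)/32 per week, and incidence at 44 weeks = 1 − exp(−44h).

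| At 32 weeks | h per week | At 44 weeks | Difference | Ratio |
|---|---|---|---|---|
| 2% | 0.00063 | 2.7% | 0.7 points | 1.37 |
| 20% | 0.00697 | 26.4% | 6.4 points | 1.32 |
| 30% | 0.01115 | 38.8% | 8.8 points | 1.29 |
| 50% | 0.02166 | 61.4% | 11.4 points | 1.23 |

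In the 30% row, if about 130 subjects switch and 260 continue (full retention), Avacopan Total reads (130 × 30.0 + 260 × 38.8)/390 = 35.9%, which is the risk at neither 32 nor 44 weeks.

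**4. Attrition.** Take a 24-week risk of 10%, so h = −ln(0.90)/24 = 0.00439. Without dropout the percentages are 13.1% at 32 weeks and 17.6% at 44. The protocol assumes 7% attrition over the trial. Spread evenly, a = −ln(0.93)/44 = 0.00165 per week, and observed incidence = h/(h + a) × [1 − exp(−(h + a)t)], giving 12.8% and 17.0%. For dropout to cancel the gap, a fraction q of the continuing groups would have to leave in Period 1, at week 6 on average: q = (0.1757 − 0.1311)/(0.1757 − 0.0260) = 0.30.

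**5. Hazard that falls after the first dose.** Let the hazard halve every L weeks, with a 32-week incidence of 10%. The crude ratio is incidence at 44 weeks over incidence at 32. The rate ratio compares first events per person-time at risk in the two windows, where person-time is the integral of the event-free proportion.

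| L | Crude ratio, 44 vs 32 weeks | Rate ratio, continuing vs switched |
|---|---|---|
| 4 weeks | 1.00 | 0.73 |
| 8 weeks | 1.04 | 0.76 |
| 12 weeks | 1.09 | 0.80 |

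For L = 4, mean time at risk is 29.35 weeks in the switched groups and 40.15 in the continuing groups, and about 10.0% have an event in each. At 52.18 weeks per year that is 17.8 against 13.0 per 100 patient-years. So when events cluster early the crude percentages are nearly right, and an exposure-adjusted rate alone would make the continuing groups look 20% to 27% safer at identical risk since first dose.

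**6. Common window.** If every group is cut at the same number of weeks from first avacopan dose, equal risk gives equal incidence whatever the shape of the hazard, apart from selection and dropout.

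**The case against.** The strongest reply is that like-for-like tables are already planned. Within Period 1 every group has 12 weeks; within Period 2 every sequence has 24 weeks plus follow-up. Events are assigned to the treatment received in the period of onset, and the listings carry onset dates. This stands. A reader might infer that the plan as a whole cannot separate early events from longer observation. It can do so in part: Period 1 can be read against Period 2 in the continuing groups, and new starters against continuers within Period 2. What those tables do not give is cumulative incidence on an aligned clock, because subject percentages from two periods cannot be added and switched subjects start their clock 12 weeks later.

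A reader might also infer that the primary safety objective is compromised. It is not. That objective compares avacopan with placebo (Protocol 2.1), and the Period 1 table serves it with equal windows. Nor does the SAP propose to set Avacopan Total against the 12-week placebo column; the combined table has no placebo column.

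The columns are split by sequence, so the label tells a careful reader that exposure differs, and the 10 mg against 30 mg contrast within each pair has equal planned time. This also stands, and it limits the problem to switched against continuing columns and to the pooled total.

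Finally, the documents describe one early signal: lymphopenia in the first 2 weeks in vasculitis patients also given cyclophosphamide or rituximab (Protocol 11.2). For such events the gap would be small. The display shells are a separate document (SAP Sponsor Approval Form) and may contain more than the text.

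**Conclusion.** The point holds as a reporting weakness of one cumulative display. At equal risk since first dose and similar retention, the continuing columns will tend to show higher percentages than the switched columns. Under a constant hazard and assumed 32-week incidences of 20% to 50%, the excess is about 6 to 11 points; for an event at 2% it is under 1 point but a ratio of 1.37. If the hazard halves every 4 to 12 weeks, the ratio is only about 1.00 to 1.09.

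Two stronger readings go too far. One is that the continuing groups would look worse purely because they were watched longer. Switched subjects are by definition Period 1 completers, while the continuing columns include Period 1 dropouts, so selection also shapes the contrast, in a direction the documents do not settle. The other is that this is the trial's only cumulative safety display. SAP IX.B also plans shifts to the highest laboratory grade during the study period.

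The conclusion rests on the inference that the combined tables hold adverse events, on the missing end to the event window, and on assumed incidences.

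**What to change.** In the All Avacopan adverse event tables:

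- Keep the crude n (%).
- State when the all-avacopan event window ends.
- Print patient-years at risk in each column header.
- Add subjects with a first event per 100 patient-years from first avacopan dose, with 95% CI, for any treatment-emergent event, serious events, events leading to drug withdrawal, and each event of special interest.
- Add incidence over a common window from first avacopan dose, for example the first 24 weeks, for all four groups. The rate should not stand alone, because it assumes a roughly constant hazard and would understate risk in the longer-observed groups if events cluster early.

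The cost is one derived time-at-risk variable and a few extra rows; dosing dates are already derived under SAP VII.C. Conduct, hypotheses and alpha do not change. The change does not remove the selection of Period 1 completers, which a footnote should state. I would label this a cheap improvement.

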A score of 3 or less signifies mild HS, a score of 4-10 signifies moderate HS and a score of 11 or higher signifies severe HS.

```
Reduction in IHS4 = Baseline Score - Post Baseline Score

% Reduction in IHS4 = 100 * Reduction in IHS4/Baseline Score
```

5) Change from Baseline in inflammatory nodule count at Week 12.

Change from Baseline = Week 12 Count - Baseline Count

6) Change from Baseline in abscess count at Week 12.

Change from Baseline = Week 12 Count - Baseline Count

Change from Baseline in draining fistula count at Week 12.

Change from Baseline = Week 12 Count – Baseline Count

 Change from Baseline to Week 12 in the modified Sartorius score to quantify the severity change of HS.

Twelve body areas will be evaluated at visits specified in the Study Schedule to calculate the Sartorius (in other efficacy endpoints) and modified Sartorius [2009] scores:

- left and right axillae,
- left and right inframammary areas,
- intermammary area,
- left and right buttocks,
- left and right inguino-crural folds,
- perianal area and perineal area, and
- other (specify).

A score of 4 indicates the least severe disease, and higher scores indicate increasingly severe disease. There is no upper limit in the score.

The presence of nodules, abscesses, fistulae, scars, and other findings will be recorded in the EDC. The longest distance between two lesions and whether lesions are separated by normal skin will also be recorded. The final Sartorius and modified Sartorius [2009] scores will be the sum of each regional score.

Change from Baseline in Modified Sartorius Score = Week 12 Score - Baseline Score

The following are the algorithms on how to calculate the Sartorius and modified Sartorius [2009] scores for each regional score:

	Sartorius (2003)	Modified Sartorius [2009]
	For each anatomic region, calculate the regional score as follows:	For each anatomic region, sum up the following to obtain the subjects score:
1	3 points per region involved.	3 points per region involved.
2	Number and scores of lesions	Numbers and scores of lesions
	2 points per nodule (or abscess) 4 points per fistula 1 point per scar	1 point per nodule (or abscess) 6 point per fistula
	1 point per "other" lesion	Note: Abscesses are considered the same as nodules since they are hard to distinguish from the other. Scars and other lesions are not considered.
3	The longest distance between two relevant lesions, or size if only one lesion	The longest distance between two relevant lesions (or size of lesion if single) in each region
	< 5 cm, 2 points < 10 cm, 4 points > 10 cm, 8 points	< 5 cm = 1 point 5-10 cm = 3 points > 10 cm = 9 points
4	Are all lesions clearly separated by normal skin? In each region yes = 0; no = 6	Are all lesions clearly separated by normal skin? In each region yes = 0; no = 9

Other Efficacy Endpoints

The following efficacy endpoints will be analyzed from Baseline to each timepoint up to Week 44, where applicable:

 Change from Baseline in inflammatory nodule count, abscess count, draining fistula count, total AN count, and non-inflammatory nodule count, nondraining and total fistula count.

Change from Baseline = Post Baseline Count - Baseline Count

 % change from Baseline in inflammatory nodule count, abscess count, draining fistula count, total AN count, and non-inflammatory nodule count, nondraining and total fistula count among subjects who have at least one corresponding lesion at Day 1.

% Change from Baseline = 100*Change from Baseline/Baseline Count

Proportion of subjects achieving HiSCR, HiSCR₇₅, and HiSCR₉₀.
 Please see the description of the Primary Endpoint for details.

% Reduction from Baseline in AN Count
$$= 100 \times \frac{\text{(Baseline AN Count - Post Baseline AN Count)}}{\text{Baseline AN Count}}$$

The proportion of subjects achieving HiSCR at Post Baseline visits will be calculated as those subjects having % Reduction from Baseline in AN count \geq 50 and (Baseline Abscess Count — Post Baseline Abscess Count \geq 0) and (Baseline Draining Fistula Count —

Post Baseline Draining Fistula Count $) \ge 0$

at Post Baseline visits divided by the total number of subjects in each treatment group.

HiSCR₇₅ or HiSCR₉₀ denotes 75% reduction or 90% reduction for the HiSCR definition instead of 50% reduction with no increase in the number of abscesses or draining fistulas count.

4) Proportion of subjects achieving at least 30% reduction and at least 1 unit reduction from Baseline in the subject's global assessment of skin pain (NRS30), in subjects with a Baseline NRS of at least 3.

Please see the description of item 2) in Secondary Endpoints for details.

% Reduction from Baseline in NRS =
$$100 \times \frac{\text{Baseline NRS-Post Baseline NRS}}{\text{Baseline NRS}}$$

The proportion of subjects achieving NRS30 at Post Baseline visits will be calculated as those subjects having % Reduction from Baseline in NRS \geq 30 and (Baseline NRS - Post Baseline NRS \geq 1) at Post Baseline visits divided

by the total number of subjects having Baseline NRS ≥ 3 in each treatment group.

5) Proportion of subjects with baseline Hurley Stage II who achieved an abscess and inflammatory nodule count of 0, 1, or 2.

Please see the description of item 4) in Secondary Endpoints for details.

The proportion of subjects with baseline Hurley Stage II achieving AN count of 0, 1, or 2 at Post Baseline visits will be calculated as those subjects having baseline Hurley Stage II and AN Count = 0, 1, or 2 at Post Baseline visits divided by the total number of subjects having baseline Hurley Stage II in each treatment group.

6) Change from Baseline in the Sartorius score, modified Sartorius score, IHS4 score, and HS-PGA to quantify the severity change of HS.

Sartorius score, modified Sartorius score, and IHS4 score has been described in items 1) and 3) of Secondary Endpoints.

The Hidradenitis Suppurativa-Physician's Global Assessment (HS-PGA) is an ordinal scale specific to HS that categorizes subjects into clear, minimal, mild, moderate, severe, or very severe disease, and it was used successfully in a phase 2 interventional clinical trial. A recently developed six stage PGA was defined as follows:

Hidradenitis Suppurativa-Physician's Global Assessment		
Score	Short	Definition
	Descriptor	
0	Clear	0 abscesses, 0 draining fistulas, 0
		inflammatory nodules, and 0 non-
		inflammatory nodules
1	Minimal	0 abscesses, 0 draining fistulas, 0
		inflammatory nodules, and only presence of
		non-inflammatory nodules
2	Mild	0 abscesses, 0 draining fistulas, and 1 to 4
		inflammatory nodules
		or
		1 abscess or draining fistula (sum of
		abscesses and draining fistulas is 1) and 0
		inflammatory nodules
3	Moderate	0 abscesses, 0 draining fistulas, and ≥ 5
		inflammatory nodules
		or
		1 abscess or draining fistula and ≥1
		inflammatory nodule
		or

		2 to 5 abscesses or draining fistulas (sum of
		abscesses and draining fistulas is 2 to 5) and
		< 10 inflammatory nodules
4	Severe	2 to 5 abscesses or draining fistulas and ≥10
		inflammatory nodules
5	Very severe	>5 abscesses or draining fistulas (sum of
		abscesses and draining fistulas >5)

HS-PGA is collected from the "Hidradenitis Suppurativa-Physician's Global Assessment (HS-PGA)" CRF.

Change from Baseline in Score = Post Baseline Score - Baseline Score

 Change from Baseline in subject-reported outcomes: SF-36 v2, EQ-5D-5L, HiSQOL and DLQI.

The SF-36v2, is the most widely used health-related quality-of-life measure in research to date. It measures the following 8 health domains as rated by the subjects over the past four weeks: Physical Functioning, Role Physical, Bodily Pain, General Health, Vitality, Social Functioning, Role Emotional, and Mental Health.

The SF-36 Physical and Mental Component Summary scores (PCS and MCS, respectively) are used to measure the two broad components, or aspects, of health-physical and mental. PCS and MCS are based on the aggregate of 8 health concepts described above and all of the 8 health domain scales are used to score both components summary measures.

One additional item asks respondents about health change over the past year.

The SF-36 will be used using Quality Metric's Health Outcomes[™] Scoring Software. The software uses updates 2009 U.S. population norms and applies a Full Missing Score Estimation (Full MSE) method as follows:

- A health domain score (except the PF domain) will be estimated provided that at least one non-missing response is available within that domain
- For the PF domain item response theory will be used to develop a model for estimates of the missing score
- Regression methods are then applied to estimate the PCS and the MCS on the basis of the available domains.

The EQ-5D-5L (EuroQuality of Life-5 Domains-5 Levels) is a self-assessed, health related, quality of life questionnaire. The scale measures quality of life on a 5-component scale including mobility, self-care, usual activities, pain/discomfort, and anxiety/depression. Each level is rated on scale that describes the degree of problems ranging from 1 to 5 in that area: no problems, slight problems, moderate problems, severe problems,

and extreme problems. EQ-5D-5L health states, defined by the EQ-5D-5L descriptive system, will be converted into a single index value.

This tool also has an overall health scale called visual analog scale where the rater selects a number from 0 (worst health state possible) to 100 (best health state possible).

The Hidradenitis Suppurativa Quality of Life (HiSQOL) is a simple, subject-administered, quality-of-life questionnaire that covers 9 domains including physical functions, activities of daily living, clothing choices due to HS, symptoms due to HS, emotional consequences, sexual functioning, social consequences, concentration consequences, and influences on work and study as assessed over the past 7 days. The HiSQOL index has been developed as an HS-specific instrument to measure the impact of HS on subjects' quality of life. Forms for these instruments will be completed by study subjects at visits specified in the Time and Events Table.

The scoring of each answer for the HiSQOL is as follows:

HiSQOL Scoring	
Response	Score
Extremely/	4
Unable to do due to my HS	
Very much	3
Moderately	2
Slightly	1
Not at all/	0
I do not normally do this/	
I am not sexually active/	
I do not work or study	
Question unanswered	0

The HiSQOL total score is calculated by summing the score of each question. Subscale scores are the total score for the items in each sub-domain. The higher the score, the more quality of life is impaired by hidradenitis suppurativa.

Dermatology Life Quality Index (DLQI),

The DLQI is a simple, subject-administered, 10-question, validated, quality-oflife questionnaire that covers 6 domains including symptoms and feelings, daily activities, leisure, work and school, personal relationships, and treatment, as assessed over the past week.

The scoring of each answer for the DLQI is as follows:

DLQI Scoring	
Response	Score
Very much	3
A lot	2
A little	1
Not at all	0
Not relevant	0
Question unanswered	0
Q7: 'prevented work or studying' = yes	3

Specifically:

- If one question is left unanswered this is scored 0 and the scores are summed and expressed as usual out of a maximum of 30.
- If two or more questions are left unanswered the questionnaire is not scored.
- If question 7 is answered 'yes' this is scored 3. If question 7 is answered 'no' but then either 'a lot' or 'a little' is ticked this is then scored 2 or 1. If "Not relevant" is ticked, the score for Question 7 is 0. If it is answered 'no', but the second half is left incomplete, the score will remain 0.
- If two or more response options are ticked, the response option with the highest score should be recorded.
- If there is a response between two tick boxes, the lower of the two score options should be recorded.

The DLQI is calculated by adding the score of each question. The maximum score is 30, and the minimum score is 0. The higher the score, the more quality of life is impaired.

Meaning of DLQI Scores

0-1 = no effect at all on subject's life

2-5 = small effect on subject's life

6-10 = moderate effect on subject's life

11-20 = very large effect on subject's life

21-30 = extremely large effect on subject's life

Change from Baseline in Score = Post Baseline Score - Baseline Score

8) Proportion of subjects who experienced flare, defined by at least a 25% increase in AN counts with a minimum increase of 2 AN counts relative to Baseline

The AN count is the sum of all abscesses and inflammatory nodules counts across all regions.

% Increase in AN counts

$$= 100 \times \frac{\text{(AN Counts at Day x} - \text{AN Counts at Baseline)}}{\text{AN Count at Baseline}}$$

The proportion of subjects who experienced flare at Post Baseline visits will be calculated as those subjects having % Increase in AN counts ≥ 25 and (Post Baseline AN Counts – Baseline AN Counts) ≥ 2 at Post Baseline visits divided by the total number of subjects in each treatment group.

9) Duration of flare in days (Observed case only)

> Duration of flare in days is calculated from the day when flare is observed to the day prior to the observation that flare is no longer present; of note, there could be multiple periods that flares are observed, in which case, the total days from the multiple periods will be used.

10) Proportion of subjects who experience at least 25% increase in draining fistula counts with a minimum increase of 2 draining fistula counts relative to Baseline.

% Increase in Draining Fistula Counts

The proportion of subjects who experienced at least 25% increase in draining fistula counts with a minimum increase of 2 draining fistula counts relative to Baseline at Post Baseline visits will be calculated as those subjects having % Increase in Draining Fistula Counts > 25 and

(Post Baseline Draining Fistula Counts —

Baseline Draining Fistula Counts) ≥ 2 at Post Baseline visits divided by the total number of subjects in each treatment group.

11) During Period 2, proportion of subjects with a loss of response, (LOR) defined as loss of at least 50% of AN count improvement achieved at Week 12 from Period 1.

AN in Period 2 – Week 12 AN $> \frac{1}{2}$ (Baseline AN – Week 12 AN)

i.e., AN in Period 2 > $\frac{1}{2}$ (Baseline AN +Week 12 AN)

Proportion of subjects with a LOR in Period 2 is calculated as those subjects having AN Counts in Period 2 $> 0.5 \times$ (Baseline AN counts —Week 12 AN counts) divided by the total number of subjects in each treatment group in Period 2.

12) Time to LOR during Period 2.

For subjects with LOR, time to LOR (days) = date of LOR – date of the first dose of study drug in Period 2 + 1; For Subjects without LOR or lost follow-up, subjects will be censored at the date of the last assessment of number of HS lesions, i.e., time to LOR (days) = date of last assessment of number of HS lesions – date of the first dose of study drug in Period 2 + 1.

 Proportion of subjects who received add-on antibiotic or other therapy for HS during Period 1 and Period 2 separately.

Add-on antibiotic or other therapies for HS are captured in the Concomitant Medication CRFs.

Proportion of subjects who received add-on antibiotic or other therapy will be calculated as those subjects who received add-on antibiotic or other therapy documented in the CM CRF post baseline divided by the total number of subjects in each treatment group in the safety population.

14) Proportion of subjects who start disallowed opioid pain therapy during Period 1 and Period 2 separately.

Oral and transdermal opioid analgesics (except for tramadol) for any reason are disallowed. Disallowed opioid pain therapy are captured in the Concomitant Medication (CM) CRFs.

Proportion of subjects who start disallowed opioid pain therapy will be calculated as those subjects who start disallowed opioid pain therapy documented in the CM CRF post baseline divided by the total number of subjects in each treatment group in safety population.

15) Proportion of subjects who undergo lesion intervention due to HS during Period 1 and Period 2 separately.

Lesion intervention due to HS is collected in AE and Concurrent Procedures CRFs.

Only two types of interventions are allowed: injection with intralesional triamcinolone acetonide suspension (intralesional Kenalog® rescue injections, i.e., triamcinolone acetonide, 10 mg total maximum per subject within a period no longer than 1 week) and incision and drainage. Any disallowed lesions interventions due to HS other than the two types described above will also be counted as "Lesion intervention due to HS" and will be recorded as major (=CSR reportable) protocol deviation.

During Period 1, a total of two protocol-allowed interventions are permissible. An intervention can occur on maximally two different lesions at the same visit or on the same lesion at two different study visits. The same lesion cannot be treated two times at the same visit. If a subject requires more than two interventions within the first 12 weeks, then they must discontinue taking blind study medication. However, these subjects will be requested to remain in the study and to complete all study procedures if possible.

During Period 2, maximally two interventions every 4 weeks are permitted. An intervention can occur on two different lesions at the same visit or on the same lesion at two different study visits. Within each 4-week period, the same type of intervention cannot be used two times on the same lesion. If a subject requires more than two interventions within a 4-week period or has two of the same interventions on the same lesion within that period, the subject must discontinue taking blind study medication. However, these subjects will be requested to remain in the study and to complete all study procedures if possible.

Proportion of subjects who undergo lesion intervention due to HS will be calculated as those subjects who have lesion intervention due to HS documented in the AE/Concurrent Procedure CRF post baseline divided by the total number of subjects in each treatment group in the safety population.

Proportion of subjects who received oral antibiotic rescue therapy will be calculated as those subjects who received oral antibiotic rescue therapy documented in the CM CRF post baseline divided by the total number of subjects in each treatment group in safety population.

16) Number of lesion interventions due to HS during Period 1 and Period 2 separately.

Lesion intervention due to HS is collected in Concurrent Procedures CRFs. Number of lesion interventions due to HS per subject will be calculated by period.

17) Health-economic information:

 a. WPAI:SHP: Change from Baseline to each timepoint during Period 1 and Change from Week 12 to each timepoint during Period 2 and including the follow-up period; Work Productivity and Activity Impairment Questionnaire (WPAI:SHP) assesses the effect of general and specific health conditions on productivity losses. Scores are calculated for four areas: percent work time missed due to HS, percent impairment while working due to HS, percent overall work impairment due to HS, and percent activity impairment due to HS. Forms for this instrument will be completed by study subjects at visits specified in the Time and Events Table to measure changes from baseline in work productivity and activity impairment.

 Hospitalizations (cumulative) by period: Number of Hospitalizations total and due to HS, Number of days hospitalized, Number of days missed from work.

Hospitalizations are captured in Heath Economics Information CRFs, cumulative number will be calculated by sum of the numbers from each visit.

 Emergency or Urgent Care visits (cumulative) by period: Number of visits total and due to HS, Number of days (or hours where applicable) missed from work.

Emergency or Urgent Care visits are captured in Heath Economics Information CRFs, cumulative number will be calculated by sum of the numbers from each visit.

d. Lesion interventions for HS by period: Number of days (or hours where applicable) missed from work due to HS lesion interventions.

Lesion interventions for HS are captured in Heath Economics Information CRFs, cumulative number of days missed from work due to HS lesion interventions will be calculated by sum of the numbers from each visit.

C. General Approach

Lesions that received intervention (incision and drainage, or intralesional injection of corticosteroid) will be counted as permanently present from the date of the intervention.

In order to adjust for the impact of major protocol disallowed treatments on the results of the trial, efficacy assessments obtained after the start of major protocol disallowed treatments will be excluded from the analysis (unless otherwise specified). Subject will be counted as non-responders for the categorical variables and have their last observation carried forward for continuous variables.

Concomitant therapy that would qualify as a rescue medication will be reviewed prior to database lock.

